3.1.1 Scheduled study visits

Recruitment of patients will occur during initial contacts with the study coordinator [name] who will present the parents with the opportunity to enroll in the study, and when general information will be given about the study on timeline, procedures involved, tests, costs.

After agreeing in principle to participate in the study, parents and child will be scheduled for **Visit 0**, at which the patients' blood is drawn for testing, questionnaires are completed, the patient is evaluated by the child therapist and is randomized for receiving treatment A (UCB infusion) or B (noninvasive treatment), and the necessary arrangements are made for UCB release from the respective banking site.

Visit 1 is scheduled within 7-14 days from V0, and during this study visit the child will receive either treatment A or B. Treatment B (noninvasive) is administered daily for 6 weeks, and is followed by 2 weeks with no treatment (washout period)

Visit 2 follows at 8 weeks distance from V1, which includes the 2 week washout period after the first treatment is administered. New blood tests are performed, also questionnaires and evaluation by child therapist, and the other treatment in sequence is administered.

Visit 3, Visit 4, and Visit 5 are scheduled at 16, 24 and 52 weeks after first treatment was administered (V1) and involve the neuropsychological evaluation of the child by the therapist and with the 3 questionnaires; brain imaging is recommended at 52 weeks

	Visit 0	V1	V2 (+ 8 weeks)	V3 (+16 wks)	V4 (+24 wks)	V5 (+52 wks)
Labs	CBC, LFTs, Els, HLA; IP	HLA MB	CBC, LFTs, Els, HLA; IP; MB			
Imagis-tics	MRI/CT					MRI/CT
Neuro/Psi Evaluation	M-CHAT-R; Q-CHAT; CAST; - Child therapist	x	M-CHAT-R; Q-CHAT; CAST; - Child therapist	M-CHAT-R; Q-CHAT; CAST; - Child therapist	M-CHAT-R; Q-CHAT; CAST; - Child therapist	M-CHAT-R; Q-CHAT; CAST; - Child therapist
Treatment started	randomi-zation	A/B	B/A	X	X	X

CBC – complete blood count with differential; LFTs – liver function tests, Els – electrolytes; IP – Inflammatory panel – ex ESR, CRP, serum protein electrophoresis, neopterin, IL-6; HLA – Typing of patient HLA- A, HLA-B, HLA-DR; MB - microbiology

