4 STUDY MEASUREMENTS AND ENDPOINTS

In this study the following endpoints will be measured/recorded

1. Efficacy - difference in the scores on the questionnaires M-CHAT, Q-CHAT and CAST before and after each treatment

2. Safety – type, severity, duration, treatment and amelioration of each of the adverse effects occurring during respective treatments.

4.1 Primary Safety Endpoints.

–

1. Adverse events (type and frequency)
2. Physical examination parameters (body mass, height, etc)
3. Vital signs: blood pressure, heart rate, respiratory rate, body temperature
4. Laboratory tests
 - HLA testing by genetic sequencing
 - Haematology: CBC - RBC, HB, MCHC, MCH, MCV, RDW, Hct, Hb, WBC Differential count –lymphocytes monocytes, neutrophils, eosinophils, basophils, flowcytometry - CD34+, TNC, viability %
 - Microbiology – presence and sensitivity of pathogens
 - LFTs Serum - Bilirubin (total and conjugated) AST, ALT, GGT, LDH, glucose
 - IP – serum protein electrophoresis, ESR, CRP, fibrinogen
 - Els - sodium, potassium, chloride, calcium, magnesium.

4.2 Measurements at each visit.

See section 3.1.1 for the visit schedule.

Visit 0: Screening Visit

Patients will be examined within 14 days prior to the first ingestion of the investigational products to assess their eligibility to participate. For each child both parents will consent in writing (Appendix 1, Informed Consent Form) to the screening process before the start of the examination. The consent form will also include the study information leaflet.

The examinations and investigations will include:

- Medical history, including history of past use of medications, demographics (date of birth, sex, race) and ASD diagnosis.
- Physical examination including assessment of general appearance, cardiovascular, lungs, mouth, throat and abdomen and measurement of height and body weight. The examination will be made in accordance with the normal clinical routines at the trial center.
- Vital signs: systolic and diastolic blood pressure in supine (after 5 minutes rest) and standing positions (1minute), pulse, respiratory rate and oral temperature.
- Laboratory tests: HLA, Haematology, (see section 4.4.3.2); baseline plasma levels of IP, Els, LFTs (these can be drawn also at V1 if considered by the study PI)

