Based on the results of the testing with the M-CHAT-R, Q-CHAT and CAST questionnaires and the evaluation from child psychologist, a recommendation for treatment will be made for either UCB administration or the noninvasive treatment for 6 weeks

Visit 1: The first treatment is administered

- The pre-dose safety assessments and eligibility checks will be recorded on the relevant pages in the individual CRFs.
- The parents will also be given the 3 questionnaires and instructed on how to complete it.
- The parents will be issued with prescriptions for trial medication, explained how to take the medication and given next appointment date; or
- The UCB infusion is administered

Visit 2: Second Treatment is administered

For these visits the examinations and investigations will include:

- Physical examination (as for visit 1)
- Vital signs: systolic and diastolic blood pressure in supine, pulse, respiratory rate and oral temperature.
- Laboratory tests
 - HLA testing by genetic sequencing
 - Haematology: CBC - RBC, HB, MCHC, MCH, MCV, RDW, Hct, Hb, WBC
 - Differential count –lymphocytes monocytes, neutrophils, eosinophils, basophils,
 - flowcytometry - CD34+, TNC, viability %
 - Microbiology – presence and sensitivity of pathogens
 - LFTs Serum - Bilirubin (total and conjugated) AST, ALT, GGT, LDH, glucose
 - IP – serum protein electrophoresis, ESR, CRP, fibrinogen
 - Els - sodium, potassium, chloride, calcium, magnesium.

Note: For any patient in which any of the above tests indicated levels outside the normal range, a follow-up visit (visit A-C) will be scheduled for an appropriate time (1 or 3 months post visit). All or the above tests will be repeated at this visit.

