Annex 3 M-CHAT-R Questionnaire

www.m-chat.org

Child's name _____ Date _____
Age _____ Relationship to child _____

M-CHAT-RTM (Modified Checklist for Autism in Toddlers Revised)

Please answer these questions about your child. Keep in mind how your child usually behaves. If you have seen your child do the behavior a few times, but he or she does not usually do it, then please answer no. Please circle yes or no for every question. Thank you very much.

1. If you point at something across the room, does your child look at it? Yes No
(FOR EXAMPLE, if you point at a toy or an animal, does your child look at the toy or animal?)
2. Have you ever wondered if your child might be deaf? Yes No
3. Does your child play pretend or make-believe? Yes No
(FOR EXAMPLE, pretend to drink from an empty cup, pretend to talk on a phone, or pretend to feed a doll or stuffed animal?)
4. Does your child like climbing on things? Yes No (FOR EXAMPLE, furniture, playground equipment, or stairs)
5. Does your child make unusual finger movements near his or her eyes? Yes No
(FOR EXAMPLE, does your child wiggle his or her fingers close to his or her eyes?)
6. Does your child point with one finger to ask for something or to get help? Yes No
(FOR EXAMPLE, pointing to a snack or toy that is out of reach)
7. Does your child point with one finger to show you something interesting? Yes No
(FOR EXAMPLE, pointing to an airplane in the sky or a big truck in the road)
8. Is your child interested in other children? (FOR EXAMPLE, does your child watch Yes No
other children, smile at them, or go to them?)
9. Does your child show you things by bringing them to you or holding them up for you to Yes No
see – not to get help, but just to share? (FOR EXAMPLE, showing you a flower, a stuffed
animal, or a toy truck)
10. Does your child respond when you call his or her name? (FOR EXAMPLE, does he or she
look up, talk or babble, or stop what he or she is doing when you call his or her name?)
Yes No
11. When you smile at your child, does he or she smile back at you? Yes No
12. Does your child get upset by everyday noises? (FOR EXAMPLE, does your
child scream or cry to noise such as a vacuum cleaner or loud music?)
Yes No
13. Does your child walk? Yes No
14. Does your child look you in the eye when you are talking to him or her, playing with him Yes No
or her, or dressing him or her?

15. Does your child try to copy what you do? (FOR EXAMPLE, wave bye-bye, clap, or Yes No make a funny noise when you do)

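### Parents are given written-in instruction on the questionnaires at Visit 1, after the Visit 0 forms; if Visit 0 is the baseline, any instruction effect falls in period 1 only (minor)

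*Combined protocol and SAP*

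**What the plan says.** All references are to the combined protocol and SAP.

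- **Section 3.1.1, Visit 0:** "questionnaires are completed, the patient is evaluated by the child therapist and is randomized". The schedule table lists the three instruments at this visit.
- **Section 4.2, end of the Visit 0 text:** a treatment recommendation is made "Based on the results of the testing with the M-CHAT-R, Q-CHAT and CAST questionnaires and the evaluation from child psychologist". The Visit 0 scores are therefore in use before the first treatment.
- **Section 4.2, Visit 1:** "The parents will also be given the 3 questionnaires and instructed on how to complete it". No other place in the documents describes instruction.
- **Section 3.1.1, table, neuropsychological row, V0 to V2:** "M-CHAT-R; Q-CHAT; CAST; - Child therapist x M-CHAT-R; Q-CHAT; CAST; - Child therapist". The V1 cell holds only an undefined x.
- **Section 3.1.1, Visit 2:** "New blood tests are performed, also questionnaires and evaluation by child therapist, and the other treatment in sequence is administered".
- **Section 4, efficacy endpoint:** "difference in the scores on the questionnaires M-CHAT, Q-CHAT and CAST before and after each treatment". The visit that supplies the first treatment's baseline is not named.
- **Synopsis and sections 5.1 and 5.2:** ANOVA is named, with no period or sequence term. Section 3.3.2 gives random order without a ratio or blocking.

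**The concern.** Efficacy rests on parent-completed scores in an open-label crossover. If instruction alters how parents answer, the measurement procedure changes once, between Visit 0 and Visit 2. That change would be counted as part of the effect of whichever treatment came first. By Visit 1 the family also knows the allocation, and families starting with the noninvasive treatment would be instructed at the visit where that treatment is explained.

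Two results could be affected: each treatment's own before/after change, and the comparison between treatments, which is the primary objective in section 2.

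**Working it through.** **Order of events.** Section 3.1.1 says "Visit 1 is scheduled within 7-14 days from V0"; section 3.3.1 gives 14 to 21 days, and the two need reconciling. On either figure the Visit 0 forms come at least a week before the written instruction. In the table's treatment row, an X stands at V3 to V5, where no treatment starts. The x at V1 in the neuropsychological row therefore most naturally means no assessment. On that reading the baselines are Visit 0 (period 1, before instruction) and Visit 2 (period 2, after it).

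**The plan's own figure.** Section 5.1 gives at least 25 children for alpha 0.05 and 80% power, without an effect size or SD, so it cannot be reproduced. Solved backwards (two-sided), it implies a within-child standardised difference of (1.960 + 0.842)/√25 = 0.560, or 0.584 with a paired t-test.

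**Inputs for the shift.** N = 25, split 13/12 by sequence. Assumed, because the documents give nothing: instruction moves the score by D points, the SD of a before/after change is 2, 3 or 4 points, errors in the two periods are independent, and there is no true effect. A is cord blood and B is the noninvasive treatment.

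**One treatment's own change.** The mean change carries D × 13/25 = 0.52 D for the treatment given first to 13 children, and D × 12/25 = 0.48 D for the other.

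**A minus B, period ignored.** D enters with a plus sign in children who had A first and a minus sign in the rest, so bias = D × (n_AB − n_BA)/N:
- 13/12: 0.04 D
- 15/10: 0.20 D
- 17/8: 0.36 D

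With period in the model, A minus B is the average of the two sequence means, (D − D)/2 = 0.

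Simulated rejection rates at two-sided 0.05 with a 13/12 split (%; SD = 2 / 3 / 4; at least 40,000 trials per cell):

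| D (points) | One-sample test, one treatment | Paired A minus B, period ignored |
|---|---|---|
| 0.25 | 6 / 6 / 5 | 5 / 5 / 5 |
| 0.5 | 9 / 7 / 6 | 5 / 5 / 5 |
| 1 | 22 / 12.5 / 9 | 3.8 / 4.6 / 4.6 |
| 2 | 61–62 / 34 / 22 | 1.8 / 3.1 / 3.8 |

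Simulation error is a few tenths of a percentage point (the 9% cell ranged from 9.2 to 9.5% between runs).

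**Power for A minus B near balance, period ignored.** Let δ be the shift in units of the SD of the within-child A minus B difference. An unmodelled period effect inflates that SD by about √(1 + δ²). Nominal 80% power then falls to about 78%, 71% and 51% for δ = 0.25, 0.5 and 1. This approximation is slightly pessimistic: direct simulation at 13/12, with the small bias in the direction of the true effect, gives 80%, 76% and 57%.

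**Marked imbalance, period ignored.** At 17/8 the type I error for A minus B is about 6.4%, 10.1% and 17.1% for the same δ. Under simple randomisation of 25 children, a split at least that uneven has probability 1 − 0.892 = 0.108. The expected absolute imbalance is 0.16, giving an expected absolute bias of 0.16 δ.

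**The case against.** Several objections carry weight.

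- **Instruction at Visit 0 is not ruled out.** The Visit 0 list in section 4.2 omits the questionnaires altogether, although section 3.1.1 has them completed then. The list is incomplete, and its silence does not prove that parents were unguided. This stands.
- **The forms instruct by themselves.** The M-CHAT-R rule for behaviour seen only a few times, "but he or she does not usually do it, then please answer no", is printed at the head of the form in Annex 3. CAST and Q-CHAT also carry printed directions. What the Visit 1 step adds is not stated. This stands, and it argues for a small D.
- **The baseline could be Visit 1.** If the forms handed out then were completed before treatment and used as baseline, the effect would vanish. No section says so and the table points the other way, but the documents leave it open.
- **The one-sample test is not the stated analysis.** The plan names ANOVA, and the primary objective is comparative. This also stands.

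A reader might infer that the first treatment's change score is known to contain an instruction effect, or that the trial's false-positive rate is 20% or more. The documents support neither. The existence of a shift is an assumption, and the high percentages belong to a single-treatment test with assumed shifts of 1 to 2 points. At 13/12 the A minus B test shows no inflation. Nor is one named treatment favoured, because order is random.

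What survives is the sequence as written, an unnamed period-1 baseline, and an analysis with no stated period term.

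**Conclusion.** The point holds in a limited, conditional form, and its severity is minor. As written, the only instruction step follows the Visit 0 forms and precedes the period-2 baseline. If Visit 0 is the baseline and instruction shifts answers, the shift is a period effect.

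- **Each treatment's own before/after change** carries about half the shift even with balanced sequences.
- **The A minus B comparison** is almost unbiased near balance; there the cost is some power if period is left out. Bias becomes material only with marked sequence imbalance and no period term.

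This rests on assumed values of D and the SDs. A point also means different things on the three instruments (20 yes/no items, 37 yes/no items and 25 multi-level items). The cancellation further assumes the same shift in both sequences; otherwise half the difference between the two shifts would remain even with period modelled. Nothing in the documents indicates that they differ.

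**What to change.** 1. In section 4.2, move the instruction step from Visit 1 to Visit 0, before the baseline forms are completed and before allocation is revealed. Use the same instruction at Visits 2 to 5.
2. Reconcile the Visit 1 text with the table in section 3.1.1, and define the x.
3. In section 4, name the baseline visit for each period: Visit 0 for the first and Visit 2 for the second.
4. In section 5, include period in the crossover ANOVA.

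The cost is a few sentences and a short standard instruction to reuse, with no added visit or staff. The period term uses one degree of freedom: the effect detectable with 25 children at 80% power moves from 0.584 to 0.585 SD. The change is worth making whatever the true size of the shift.

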4.3 Specific detail on measurements

4.4.1 Adverse events

An adverse event is the development of an undesirable medical condition - e.g. symptoms or abnormal results of an investigation - or the deterioration of a pre-existing medical condition (not relevant in this study). AE's will be collected by means of a standard question: "Have you had any health problems since the previous visit?" AE's will be recorded at every visit. Spontaneously reported AE's and/or observed AE's and the subject's response to this question will be recorded on the AE form with information about seriousness, action taken, date of onset and recovery, maximum intensity and outcome. The subjects will be asked to assess the intensity of the reported Adverse Event according to the following scale:

Mild = awareness of sign or symptom, but easily tolerated
Moderate = discomfort sufficient to cause interference with normal activities
Severe = incapacitating, with inability to perform normal activities.

A Serious Adverse Event is an adverse event occurring during any phase of the study and at any dose of the investigational product or placebo, which fulfils one or more of the following criteria:

- Results in death;
- Is immediately life-threatening;
- Requires in-subject hospitalization;
- Results in persistent or significant disability or incapacity.

The causality of Serious Adverse Events (i.e. the relationship to study treatment) will be assessed by the investigators, who in completing the relevant Case Report Form must answer ‘yes’ or ‘no’ to the question “Do you consider that there is a reasonable possibility that the event may have been caused by the study medication?” The following factors should be considered when deciding if there is a “reasonable possibility” that an Adverse Event may have been caused by the investigational product.

- Time course of events and exposure to suspect drug – did the AE occur in a reasonable temporal relationship to the administration of suspect drug?
- Dechallenge experience – did the AE resolve or improve on stopping or reducing the dose of the suspect drug?
- Rechallenge experience - did the AE reoccur if the suspected drug was reintroduced after having stopped?
- Laboratory tests – has a specific laboratory investigation confirm the relationship?
- No alternative cause - the AE cannot be reasonably explained by another aetiology such as an underlying disease (not previously present), other drugs or environmental factors.

There would not be a “reasonable possibility” of causality if none of the above criteria apply or where there is evidence of exposure and a reasonable time course, but any dechallenge is negative or there is another more likely cause of the AE.

In this study the Adverse Events will be noted from the interview at the time of visit and from the daily input in the diary.

4.4.2 12- Lead ECG

Standard 12-lead ECGs will be performed at the indication of the anesthesiology doctor if necessary.

The Bioclinica Laboratory will perform all the clinical laboratory investigations.

The samples will be processed and shipped as per instructions of the pathology laboratory.

For all laboratory investigations the investigator will receive actual printouts of the data from the Laboratory. A signed original printout will be attached to the CRF and a copy thereof will be filed in the subject file. The reference ranges will be provided in the clinical trial manual (investigator’s file) together with the descriptions of the laboratory methods used. The laboratory will provide normal ranges on each report to ease the investigator’s assessment.

As part of the overall safety monitoring plan, the safety monitor ([name]) will also assess the data, particularly those falling outside the normal range.

The blood samples will always be taken before the first trial medication dose for that day is taken. The blood samples will be collected in tubes labeled with the following information: patient name; test type (HLA, biochemistry, hematology, flowcytometry); blood sample number (visit 2, 3,4 or 5) and sampling time.

Blood samples will be handled according to the protocols for testing of the respective laboratories

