ENDPOINTS:	
EFFICACY
 
 1. Behavioral improvement with the validated scales for autistic spectrum disorders 2. Examination by child psychologist 
SAFETY
 
 1. Adverse events, especially frequency and intensity of agitation episodes 2. Modification of vital signs: blood pressure, heart rate, respiratory rate, body temperature. 3. Modification of laboratory tests: Haematology: RBC, MCHC, MCH, MCV, RDW, Hct, Hb, WBC Differential count –lymphocytes monocytes, neutrophils, eosinophils, basophils; CD45+; blood cultures Biochemistry: Serum - Bilirubin (total) AST, ALT, LDH, glucose, urea, creatinine, sodium, potassium, chloride, calcium., MB microbiology; IP – Inflammatory panel
SAMPLE SIZE:	at least 25 patients, optimum 40 patients enrolled
STATISTICAL ANALYSIS:	Summary statistics will describe the safety variables. Significance testing will be done using analysis of variance for continuous and chi-square test for categorical variables. ($\alpha = 0,05$)

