3. ***Lecithin 500 mg bid*** will be administered if brain imaging reveals any demyelination/myelination deficits, global cerebral atrophy or regional atrophy

4. ***Magnesium citrate with vitamin B6 (150 mg/6 mg qd)*** will be included if restlessness/agitation/anxiety is present significantly in the clinical picture

5. ***Piranoquinolinquinone (PQQ) 20 mg/day*** will be administered in situations of apathic/disinterested behavior, marked introversion, marked developmental delays

6. ***Optional medication for special situations***, with parent's clear understanding, a few other treatment options will be included – ex.

- Tecfidera (dimethyl fumarate) 60 mg bid with food (presence of hypo/demyelination with an autoimmune component); immune modulation is involved in ASD as documented in Kornberg, 2018
- Boswellia extract 400 mg bid – decreases activation of NfK-beta which is the main modulator of both inflammation and neuronal connections
- piracetam (Nootropil) 400 mg bid (presence of severe developmental delays with low motor coordination and energy levels)
- Bacopa monieri (presence of demyelination in absence of immune over-activation)
- Uridine (inflammation mitigation, mitochondrial function stimulation)
- Hipophae rhamnoides oil (source of omega-7 unsaturated fatty acids for synaptic vesicles)

The decision of which of these components should be given is taken after all tests are done and the child psychologist/therapist and the study investigator discuss the case and afterwards discuss the practical issues of administering the recommended treatment with the parents.

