2 STUDY OBJECTIVES

The primary objective of this study is to investigate the comparative efficacy of the UCB infusion and the non-invasive treatments for improving the functioning of children with ASD.

A secondary objective is to determine whether there are significant differences in the safety profiles of the two treatments administered

In addition there will be an evaluation of the structural changes in the CNS of the children with ASD, done by MRI

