3.2.1 Inclusion criteria

To be enrolled, the following criteria have to be fulfilled at Visit 2:

1. Children of either sex between 3 and 7 years.
2. Body weight between 15 and 30 kg
3. Diagnosed with ASD
4. No significant diseases or clinically significant abnormal laboratory values during screening
5. On no regular medical treatment

6. Parents able to be informed of the nature of the study and willing to give written informed consent (Consent must be obtained before any study-related procedures are conducted).

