3.2.2 Exclusion criteria

Any of the following is regarded as a criterion for exclusion from the study:

1. Hypersensitivity or allergic reaction to any drugs or supplements.
2. Any disease or condition which might compromise the haematopoietic, renal, endocrine, pulmonary, central nervous, cardiovascular, immunological, dermatological, gastrointestinal or any other body system.
3. History of allergic conditions – asthma, urticaria, eczema.
4. History or presence of dyspepsia, gastric ulcer or duodenal ulcer.
5. History of autoimmune disorders e.g. systemic lupus erythematosus, haemolytic anemia.
6. Intake of steroid medication within 7 days before start of the study
7. Presence of clinically significant abnormal laboratory results during screening.
8. Participation in a clinical study of any investigational product 1 month prior to visit 1 or during the study.

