4.4 Measurements recorded daily in a diary

A diary will be filled in at home during the entire study in the morning after taking the morning dose and at night after the evening before going to bed. The following variables will be recorded:

- i) Intake of study medication (if, time and if with food)
- ii) Occurrence of any adverse effects.
- iii) Intake of any incidental medication

The subjects will record the time (morning and evening) that the study medication has been taken. The recordings are a measurement of compliance.

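### The adverse-event definition read literally sets aside worsening of existing agitation, and Section 5.2 plans post-study laboratory results that the visit schedule does not supply

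*Combined protocol and SAP*

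**What the plan says.** **Adverse events.** Section 4.4.1 includes in its definition "the deterioration of a pre-existing medical condition (not relevant in this study"). The synopsis gives as the first safety endpoint "Adverse events, especially frequency and intensity of agitation episodes". Section 3.2.1 requires each child to be "Diagnosed with ASD". Under Study Rationale, the magnesium and vitamin B6 component "will be included if restlessness/agitation/anxiety is present significantly in the clinical picture", so agitation at entry is foreseen. Section 3.2.2 excludes "Any disease or condition which might compromise the haematopoietic, renal, endocrine, pulmonary, central nervous, cardiovascular, immunological, dermatological, gastrointestinal or any other body system". Events are collected by a standard question at each visit, by spontaneous report and observation, and in a home diary that records "Occurrence of any adverse effects".

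**Laboratory tests.** Section 2 sets as the secondary objective to determine "whether there are significant differences in the safety profiles of the two treatments administered". Section 4.1 lists laboratory tests as a primary safety endpoint, together with adverse events, vital signs and "Physical examination parameters (body mass, height, etc"). The visit table in Section 3.1.1 has laboratory entries at V0, V1 and V2 only. Its text gives V3 to V5 neuropsychological evaluation and questionnaires, with imaging at week 52. Section 5.2 plans to list and summarise findings before, during and after the study for physical examination, vital signs and laboratory variables, and it includes urinalysis.

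**The concern.** The two parts are independent, but both bear on the safety comparison.

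(i) The frequency and intensity of agitation episodes are naturally judged against the level a child already has. A definition that sets aside worsening of what was there before leaves it unclear whether more frequent or more intense agitation in an already agitated child is to be recorded. New-onset agitation is not affected.

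(ii) A crossover should give laboratory results after both treatments in each child. If the table is followed, they exist after the first treatment only. The laboratory comparison is then between sequences, on half of the treatment periods, and the post-study results promised in Section 5.2 do not exist for children who had no conditional repeat.

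**Working it through.** **(i) Adverse-event definition: the texts side by side.**
- Section 3.2.1: every child has a pre-existing condition, ASD.
- Study Rationale: some children may show significant agitation at entry.
- Synopsis: agitation frequency and intensity are emphasised under adverse events.
- Section 4.4.1: worsening of a pre-existing condition is labelled as not relevant, with no limit to comorbidities.

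Taken together and literally, worsening of existing agitation is outside the definition although it is part of what the synopsis emphasises. The documents give no rate of agitation, so no under-count can be computed.

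**(ii) Laboratory schedule.**

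Inputs: at least 25 children, optimum 40 (synopsis); Treatment B daily for 6 weeks, then 2 weeks without treatment, with V2 at week 8 (Section 3.1.1); at V2, new blood tests and then the second treatment (Section 3.1.1); blood taken before that day's first dose (Section 4.4.2). Assumption: 1:1 allocation, since no ratio is stated.

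*Routine post-treatment tests if the table is followed.* After the first treatment, at V2: 25 of 25, or 40 of 40. After the second: 0 of 25, or 0 of 40. So 25 of 50 treatment periods (or 40 of 80) have such a test. Per treatment this is 12-13 children at N=25 and 40/2 = 20 at N=40.

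*Routine tests while taking B.*
- B first: B in weeks 0-6, test at week 8, after the washout.
- A first: test at week 8 before B starts, none scheduled later.
- Total: 0.

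*Zero-event upper bound.* The one-sided 95% bound is 1 - 0.05^(1/n).

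| n | Upper bound |
|---|---|
| 12 | 22.1% |
| 13 | 20.6% |
| 20 | 13.9% |
| 25 | 11.3% |
| 40 | 7.2% |

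The last two rows show what tests after both treatments could give at best. In A-then-B children, second-period tests would follow both treatments.

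*Conditional repeats.* The note under Visit 2 in Section 4.2 provides a repeat at 1 or 3 months after an out-of-range result. Take these as about 30 and 91 days, and V0 to V1 as 7-21 days (Sections 3.1.1 and 3.3.1 give different intervals, and this spans both).
- One month after V2: week 8 + 4.3 = 12.3, within B for A-first children (weeks 8-14). Three months after V2: week 8 + 13 = 21, after B.
- If the note also covers V0: one month is day 30 - 21 = 9 to 30 - 7 = 23 after V1, within B for B-first children. Three months is day 91 - 21 = 70 to 91 - 7 = 84, or weeks 10-12, within B for A-first children.

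*Texts that do not fit the table.*
- Section 4.2 uses a plural for visits under a heading that names Visit 2 alone.
- Section 4.4.2 labels blood tubes for visits 2 to 5.
- Section 3.2.4 gives withdrawn children the Visit 5 assessments, which in the table include no laboratory tests.
- Section 5.2 names urinalysis, which no visit schedules.
- Physical examination and vital signs have no clear entry after V2, apart from vital signs around the infusion (Annex 6).

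**The case against.** **On (i).** Section 3.2.2 excludes almost every other disease, which offers an innocent explanation for the parenthesis. Section 4.4.1 counts symptoms as adverse events, and the synopsis places agitation among them. The visit question, spontaneous reports and the diary remain open. This stands: a reader might infer that worse agitation will go unrecorded, or that hospitals will record it differently, and the documents show neither. Three hospitals are named for the infusion, but nothing says that adverse events are ascertained separately at each. What survives is a stated rule that, taken at its word, excludes part of an emphasised safety endpoint.

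**On (ii).** The tube labels for visits 3 to 5 suggest that later samples may be intended, so it cannot be said that none will be taken. They schedule no test, however, and they contradict the table. Nor do the documents support saying that only a one-month repeat after V2 could fall within Treatment B. That depends on which visits the note in Section 4.2 covers.

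A reader might also conclude that the laboratory comparison can detect only very large differences. An unadjusted two-sample t-test (two-sided alpha 0.05, 80% power) gives 1.17 SD for 12 against 13 children and 0.91 SD for 20 against 20. These figures ignore the V0 values. With an assumed V0-V2 correlation r of 0.5-0.7 (not in the documents), multiplying by sqrt(1 - r^2) = 0.87-0.71 gives 1.01-0.84 SD and 0.79-0.65 SD. Section 5.2 plans listing and summary of laboratory data, and the synopsis does not assign its significance tests to them. The conclusion does not rest on the SD figures.

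**Conclusion.** Both defects hold as inconsistencies in the text and should be fixed.

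(i) The definition in Section 4.4.1 conflicts, on its literal reading, with the agitation endpoint in the synopsis. Its effect on counts is unknown.

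(ii) Section 5.2 plans laboratory results that the schedule in Section 3.1.1 does not provide. The counts and upper bounds above are firm only if the table is what will be followed and allocation is 1:1. On that basis the routine laboratory comparison is confined to the first period, and Treatment B is never observed by a routine test during dosing. If the tube labels are right instead, the table is incomplete and these consequences change. The need to reconcile the sections remains either way.

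**What to change.** (i) Delete the parenthesis in Section 4.4.1 and add one sentence: worsening of a pre-existing condition, including more frequent or more intense agitation than at study entry, is recorded as an adverse event. Cost: more adverse events will be recorded. Agitation at entry is already considered when the components of Treatment B are chosen.

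(ii) Reconcile Sections 3.1.1, 3.2.4, 4.2, 4.4.2 and 5.2.
- *If the table is right:* state that the laboratory comparison covers V0-V2 only, is between sequences and is adjusted for the V0 value, and that V2 tests in B-first children follow the washout. Remove post-study laboratory tests and urinalysis from Section 5.2, correct the tube labels, say which visits the repeat note covers, and say whether withdrawn children have tests. Make the same check for physical examination and vital signs. Cost: wording only.
- *If samples after V2 are intended:* show them in the visit table. Cost: possibly added blood draws in children aged 3-7, 25-40 draws for one extra sample per child.
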